Hypothesis 3a (Aim 3a) states that adherence will be higher in subject referred to home PR, will be tested with Fisher’s exact test supplemented with logistic regression adjusting for dyspnea MRC, age, social support, comorbidities, and FEV1. Exploratory analyses will be performed to examine how the number of rehab sessions impacts hospitalization/ED rates, CRQ dyspnea score, CRQ emotional score, and number of daily steps.

Hypothesis 3b (Aim 3b): participants on home-based PR will have higher physical (dyspnea fatigue) and, higher emotional CRQ summary scores at month three than participants who were referred to conventional PR. Tested with t-tests supplemented with linear regression models adjusting for baseline scores and dyspnea MRC, age, social support, comorbidities and FEV1.

Hypothesis 3 c (aim 3c): participants on home-based PR will have more daily PA than participants referred to conventional PR at month three. This will be measured by daily steps and minutes spent in sedentary, light, and moderate activity measured by the ActiGraph.^{30,31} This study has two activity monitors, the ActiGraph, a gold standard activity monitor used for outcome measures (7-day wearing) at baseline, 3, and 6 months; and the Garmin Vivofit PR activity monitor, which will be used daily, but will NOT be used as an outcome measure, rather for PR and health coaching and participant awareness of physical activity (participant will keep this activity monitor). Tested with Wilcoxon tests supplemented with linear regression models adjusting for baseline values and dyspnea MRC, age, social support, comorbidities and FEV1.

Hypothesis 3d (Aim 3d): individuals in the home-based PR program will have lower readmissions and ER visits compared to individual referred to conventional PR. Tested with Fisher’s exact test supplemented with logistic regression models adjusted for hospitalizations in the previous year, age, dyspnea, and comorbidities.

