For the continuous study outcomes, changes from baseline to three months will be compared between the study arms using two-sample, two-sided t-tests with 5% type I error rates. Changes in QOL, number of steps, and length of stay will be compared between the two treatment sequences using two-sample two-sided t-tests. No adjustments will be made for multiple testing. Means, SDs, medians, ranges, and frequency distributions will be reported and plotted over time by study arm. Linear models will be used to assess the impact of treatment arm on three-month outcomes after adjusting for the corresponding baseline measure and other variables related to the outcome (age, degree of breathlessness at baseline using the mMRC dyspnea, and

FEV1). Repeated measures mixed models will be used to estimate the intervention effect over the 6 months of the study (this will measure trajectory and maintenance of benefits / behavior change). Intent-to-treat analyses will also be performed to determine the sensitivity of the results to dropouts and missing values. In the intent-to-treat analyses, if a month three measure is missing for any reason, it will be described as not changing from baseline. Healthcare utilization (number of ED visits, hospitalizations, and length of stay) between baseline and three months will be treated (analyzed) as both binary (for incidence rates) and continuous (for the number of events). The binary endpoints will all be compared between groups using Fisher's exact test. Logistic regression models will also be fit to look for differences in these outcomes by arm after adjusting for age, mMRC, FEV1, baseline levels of anxiety, depression, and fear, and baseline healthcare utilization, (before starting the study) particularly hospitalizations in the previous year.

Descriptive summaries of the changes between baseline, three, six, and nine months will be used to assess the effect of the home based intervention on the control arm and the residual beneficial effect on the intervention arm. These results will be only descriptive and exploratory. No formal hypothesis testing will be done. All data will be stored in REDCap and analyzed using SAS (Cary, NC).

Per-Protocol Analysis (Dose Response): We will conduct an exploratory analysis to assess the effect of dose of PR sessions on study outcomes. This analysis will control for potential confounders of dose.

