Assessment of Bias: Potential bias due to loss to follow-up will be assessed using a time to event analysis for the association of patient characteristics with time to dropout; results will be reported and used to evaluate the robustness of the study findings. We will also conduct sensitivity analyses in which missing data for dropouts are imputed under plausible missing-not-at-random assumptions.

Missing data: A common affliction with randomized clinical trial field experiments is noncompliance with both treatment and missing study participation data. To estimate the overall treatment effect for the entire sample, an "intention to treat" analysis will be conducted, using our above likelihood-based analysis method for repeated measures, including data on all subjects who were randomized to the study group. This allows us to use all available data, rather than delete participants with missing values from the analysis of treatment effects.³⁴

Aim 4: Cost-Effectiveness Analysis

This aims to estimate the value of implementing Home PR compared to subjects referred to conventional PR. The CEA, will estimate the ratio of the average change of cost per patient divided by the average change in QALYs per patient for health coaching compared to delivering standard care. QALYs will be based on the EQ-5D-3L³⁵ using a preference-based value set derived from a sample of the US population. QALYs will be calculated by multiplying the utilities by a number of time participants spent in a particular health state. Transitions between health states will be linearly interpolated. The perspective for the CEA is that of the healthcare provider.

For both arms, all resource utilization at the health centers for the one-year period following index hospitalization discharge will be collected. Estimated costs will be standardized using a bottom-up approach. Professional services defined by Current Procedure Terminology code will be valued using national reimbursement amounts from the Medicare fee schedules. Billed charges for hospital services will be valued using department specific cost-to-charge ratios based on the hospital's annual Medicare cost report. All costs will be inflated to a common year using the Gross Domestic Product implicit price deflators.

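### CRQ and daily steps have no single lead analysis, the more efficient baseline-adjusted CRQ model is only a supplement, and intent-to-treat names two different procedures

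*Combined protocol and SAP*

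**What the plan says.** **Steps.** Under Analyses, Hypothesis 3c uses Wilcoxon tests supplemented by baseline-adjusted linear regression. The Power Statement and Statistical Analysis and Power assign t-tests to all continuous endpoints. The general paragraph that follows the hypotheses applies a t-test to the change in steps.

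**CRQ.** Hypothesis 3b expects "higher emotional CRQ summary scores at month three than participants who were referred to conventional PR". It is to be tested with t-tests, and the variable tested is not named. The t-tests are "supplemented with linear regression models adjusting for baseline scores and dyspnea MRC, age, social support, comorbidities and FEV1". The general paragraph applies two-sided 5% t-tests to change from baseline to three months. It then describes linear models for the three-month outcome, adjusted for the baseline measure and "other variables related to the outcome (age, degree of breathlessness at baseline using the mMRC dyspnea", plus FEV1. Social support and comorbidities are not in that list, and these models are given no rank relative to the t-tests.

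**Intent-to-treat.** The general paragraph says "Intent-to-treat analyses will also be performed to determine the sensitivity of the results to dropouts and missing values", and there "if a month three measure is missing for any reason, it will be described as not changing from baseline". The Missing data paragraph uses the same term for an analysis "To estimate the overall treatment effect for the entire sample", "using our above likelihood-based analysis method for repeated measures, including data on all subjects who were randomized to the study group". Assessment of Bias adds "sensitivity analyses in which missing data for dropouts are imputed under plausible missing-not-at-random assumptions".

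**Power.** Both power sections claim at least 80% power with 72 per arm for a CRQ difference of 0.5 (SD 1.0) and for 1000 steps (SD 2,000) at three months. Neither says whether the SD is that of the month-3 value or of the change.

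**The concern.** CRQ and steps carry Hypotheses 3b and 3c, in a trial that acknowledges it cannot be blinded. Two analysts following this text could report different lead p-values for the same endpoint, and different results under the name intent-to-treat. Either could cite the plan.

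The plan also leads with the less efficient CRQ analysis. A comparison adjusted for baseline uses data already collected and, with a baseline measured before randomization, is more powerful than both t-tests across the correlations considered below. Here it is only a supplement to Hypothesis 3b, and it is not one model because its covariates differ between paragraphs.

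**Working it through.** **Inputs from the documents.** 72 per arm; CRQ difference 0.5, SD 1.0; steps difference 1000, SD 2,000 (the same standardized effect, 0.5); two-sided 0.05; 75 per arm enrolled for 5% dropout. **Assumed.** The baseline-to-month-3 correlation r is not given, so 0.2 to 0.8 is used, with equal SDs at the two times and normal data.

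**1. The plan's own figure.** Noncentrality = 0.5 / (1.0 × √(2/72)) = 0.5 / 0.1667 = 3.0. With 142 degrees of freedom, power is 84.6%. The claim of at least 80% reproduces when SD 1.0 belongs to the quantity tested.

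**2. Power of the three CRQ analyses.**
- Score SD = 1.0: change SD = √(2(1−r)); adjusted SD = √(1−r²).
- Change SD = 1.0: score SD = 1/√(2(1−r)); adjusted SD = √((1+r)/2).

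Example, r = 0.2 with score SD 1.0: change SD = √1.6 = 1.265 and power 65%; adjusted SD = √0.96 = 0.980 and power 86%.

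| r | Score SD 1.0: month-3 t | Change t | Adjusted | Change SD 1.0: month-3 t | Change t | Adjusted |
|---|---|---|---|---|---|---|
| 0.2 | 85% | 65% | 86% | 96% | 85% | 97% |
| 0.3 | 85% | 71% | 88% | 94% | 85% | 96% |
| 0.5 | 85% | 85% | 93% | 85% | 85% | 93% |
| 0.7 | 85% | 97% | 99% | 64% | 85% | 90% |
| 0.8 | 85% | 99.7% | 99.9% | 47% | 85% | 88% |

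The change t-test is below 80% for r under about 0.43 (score SD 1.0), and the month-3 t-test for r above about 0.56 (change SD 1.0). Each falls short only when SD 1.0 refers to the other quantity.

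**3. Dependence on alpha.** Both power sections speak of adjusting for multiple comparisons; the general paragraph says none will be made. At an illustrative 0.025, the t-test on the scale to which SD 1.0 belongs has 77% power, and the adjusted model 79% at r = 0.2 (score SD 1.0).

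**4. How far the candidate tests disagree** (simulation, 72 per arm).
- CRQ, month-3 t-test against change t-test, true difference 0.5: different verdicts at 0.05 in 16–27% of trials (score SD 1.0) or 14–46% (change SD 1.0). With no effect, at least one is significant in about 9%.
- Steps, Wilcoxon on month-3 values against t-test on change (SD 2,000 at each time): verdicts differ in 17–27%.
- Steps, both tests on change: verdicts differ in about 0–7%. With no effect, at least one is significant in about 6%.

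**5. The no-change rule** (75 per arm, change SD 1.0, missing at random within arm, assumed control-arm recovery g of 0 to 1.0 points). With the same missing fraction m in both arms, the expected difference is (1−m)(g+0.5) − (1−m)g = (1−m) × 0.5. At m = 0.05 this is 0.475, with power 81–84% against 84% for observed cases only.

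**6. Timing of baseline.** Phase 3 (R33) randomizes at hospital discharge. Study Design and Methods takes baseline activity in the first week after discharge, a pilot procedure that Phase 3 carries forward for the home arm. Baseline steps may therefore follow assignment. Questionnaires come back in postage-paid envelopes, and the plan does not say whether baseline CRQ is completed before randomization.

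**The case against.** The strongest reply is that the CRQ text can be read as consistent: Hypothesis 3b names no test variable, the general paragraph supplies one (change), and together they give a t-test on change. The same reading makes the Wilcoxon test for steps a test on change. This stands in part. A reader might infer that the plan openly prescribes two CRQ tests, or that its error rate is 9%. The documents do not support either. The tested quantity is ambiguous, and the 14–46%, 17–27% and 9% figures apply only if the hypotheses mean the month-3 value. The error rates also require choosing the test after seeing the data. The Wilcoxon and t-test conflict for steps remains on any reading, but it is small if both use change.

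Second, the no-change rule already has a stated sensitivity role, and missing-not-at-random analyses are planned beside it. That stands: the defect is the shared name. A reader might infer that the rule biases the trial's conclusions, but at the planned 5% dropout, equal in the arms, its effect is small. Material distortion needs clearly unequal missingness together with recovery, which the documents do not predict.

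Third, the adjusted model is not subordinate everywhere. The general paragraph lists its linear models without rank, and Missing data gives the repeated-measures model the overall effect. This is also right: supplement is exact only for the hypothesis paragraphs. But the mixed model is described over six months, with no month-3 contrast or baseline handling, so it does not settle the lead.

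Fourth, a prespecified change t-test is valid if baseline precedes randomization. True, but it uses the same data less efficiently.

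**Conclusion.** The point holds as one of reconciliation and efficiency for two secondary endpoints. The steps test is contradictory, the CRQ test variable is ambiguous, the covariate lists differ, and one label covers two procedures.

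Leading with the baseline-adjusted CRQ comparison gives 86–99.9% power (score SD 1.0) or 88–97% (change SD 1.0), whereas the change t-test can be as low as 65% and the month-3 t-test as low as 47%. This rests on the assumed correlation range, alpha 0.05 and a baseline CRQ completed before randomization. It is not a guarantee of 80%: at alpha 0.025 the lowest figure is 79%. If baseline CRQ cannot be used, an unadjusted month-3 comparison has only 64% or 47% power at correlation 0.7 or 0.8 when 1.0 is the change SD.

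A reader might conclude that the sample size or the primary analysis is in doubt. Neither is: the CRQ and steps power claim reproduces at 0.05, and the Fisher test of adherence is untouched. The plan should be amended, but the validity of the trial does not depend on it.

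**What to change.** 1. **CRQ.** Make the baseline-adjusted month-3 comparison the lead, either as a linear model or as a mixed model with a month-3 contrast. Use one covariate list, reconciled between Hypothesis 3b and the general paragraph, and make the t-tests supportive. State that baseline CRQ is completed before randomization; if it is not, the power gain is not assured and should not be claimed. Settle the multiple-comparisons wording before quoting power.
2. **Steps.** Name one lead test and align the two power sections, Hypothesis 3c and the general paragraph. Decide on baseline adjustment or change only after reconciling the post-discharge baseline week with randomization at discharge.
3. **Intent-to-treat.** Reserve the term for the analysis of all randomized participants under Missing data. Give the no-change rule its own name as a sensitivity analysis.

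While editing, say whether SD 1.0 belongs to the score or the change, and how deaths enter these two analyses; the no-change rule covers a value missing for any reason.

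**Cost.** SAP wording and slightly more model specification, with no extra patients or measurements. If baseline CRQ is at present completed after assignment, its collection would have to move before randomization.

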During the consent process, the patient will have the opportunity to try the proposed home-based PR system in the hospital room, aiding in their confidence in their ability to use the system and the ease of the exercises. The study team will provide a step by step demonstration of the exercises (following the exercises on the computer tablet). The participant will be asked to rate their confidence to use the technology presented and their confidence (self-efficacy) to perform the home rehabilitation routine on a scale from 0 (no confidence) to 10

(great confidence). A rating of five or greater will be deemed an acceptable confidence level to participate in the study.

Each participant will be asked to define a particular place and time they can perform the home-based PR. The physical and mental environment is critical for the successful adoption of new behavior (PR). Participants will learn about the weekly calls with the coach to discuss their rehabilitation and monitored measures (steps, level of shortness of breath, well-being, and fatigue). They will then go over the daily answers to well-being questions (mood, breathlessness, and energy, as tested in the pilot study and shown in Fig.2; see participant software application section below). After performing the PR routine (to ensure safety and understanding) and reviewing the use of the monitors, a plan for a PR coach call, a week to 10 days after discharge. The participant will use the criterion activity monitor (Actigraph, Fig. 3) that will determine the baseline physical activity during the first week immediately after discharge to define a baseline physical activity. The coordinator will discuss the in-home activities with the participant to identify possible exercise-related fall hazards in the home environment.

[figure not shown]

Figure 2

Figure 3

Figure 4

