Phase 3 (R33): Mayo Clinic Rochester and Jacksonville Fl will participate in this Phase. After review of the first 30 participants, the remaining 120 patients with a COPD-related hospitalization (exacerbation or pneumonia) will be randomized at hospital discharge to the home-based PR or usual care (referral to conventional center-based PR). Inclusion, exclusion criteria and recruitment will be identical to the Phase 1 and 2 of the study. Randomization will be completed online through a centralized program Research Electronic Data Capture (REDCap).

The participants randomized to home-based PR will follow the same procedures in the R61 phase, plus any changes suggested by the qualitative study. Any changes will involve a protocol modification and submitted to the IRB for review.

Questionnaires and Activity Monitor: All participants will be asked to complete questionnaires and wear a small activity monitor (Actigraph) at Baseline and Months 3,6 and 12. The participants will be supplied with postage paid envelopes to return the questionnaires and activity monitor.

Questionnaires: Questionnaires include the Medical Research Council (MRC), Chronic Respiratory Questionnaire (CRQ), EuroQol-5D (EQ5D), Patient Health Questionnaire- 9 question (PHQ9), General Anxiety Disorder – 2 question (GAD2), Interpersonal Support Evaluation List (ISEL), Self-Management Ability Scale (SMAS30), Linear Analog Scale Assessment (LASA), Meaning in Life Questionnaire (MIL) and the Working Alliance Inventory (WAI). All questionnaires with the exception of the WAI will be administered at baseline and 3, 6 and 12 Month. The WAI questionnaire will be administered when the participant has completed the Health Coaching Period. For participants randomized to the Intervention arm, the WAI will be administered at 3 months. Participants randomized to the Control/Wait arm will receive the WAI at 6 months. The Charlson Comorbidity Index (CCI) will be included in the baseline questionnaire packet. The CCI will assist in summarizing the enrolled subjects in statistical models.

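### Lasting benefit of home PR is to be read from changes within each arm, with no between-arm contrast, and the control-arm effect has no defined meaning until the design is reconciled

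*Combined protocol and SAP*

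**What the plan says.** The sentence at issue is in the Analyses section of the combined protocol and SAP, after the paragraph on continuous outcomes: "Descriptive summaries of the changes between baseline, three, six, and nine months will be used". The summaries are to be "used to assess the effect of the home based intervention on the control arm and the residual beneficial effect on the intervention arm". The section then limits their status: "These results will be only descriptive and exploratory", and "No formal hypothesis testing will be done".

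Other parts of the plan bear on how this should be read:

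- **Other planned analyses (same section).** Changes from baseline to month 3 are compared between arms with t-tests, supported by baseline-adjusted linear models. Repeated-measures mixed models estimate the intervention effect over 6 months, with trajectory and maintenance as their stated purpose. Summary statistics are plotted over time by arm.
- **Baseline.** Under Study Design and Methods (Phase 1), the ActiGraph is worn to "determine the baseline physical activity during the first week immediately after discharge". Under Phase 3 (R33), patients are "randomized at hospital discharge to the home-based PR or usual care (referral to conventional center-based PR").
- **What controls receive.** Phase 2 and the Conventional PR group section give controls a referral, a follow-up call, mileage reimbursement and a Garmin monitor. Neither gives them home PR.
- **Visits.** Questionnaires and Activity Monitor schedules both measures at baseline and months 3, 6 and 12 for everyone. Aims 3b and 3c list only baseline, 3 and 6 months. Neither schedule has a month 9.
- **Signs of a wait-list.** The Questionnaires paragraph gives the Working Alliance Inventory when coaching is complete: month 3 for the intervention arm, month 6 for what it calls the Control/Wait arm. The Analyses section also refers to two treatment sequences.

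**The concern.** The sentence assigns an effect to each arm and uses only that arm's change over time to assess it. Entry requires a COPD-related hospitalization, and baseline activity is recorded in the first week at home. A baseline CRQ completed around discharge would also tend to reach back into the admission, because its fatigue, emotion and mastery items cover the previous two weeks. Some improvement afterward is plausible in both arms whether or not the program works. Patients selected at a low point also regress toward their usual level. A change from that baseline cannot separate these from a program effect. A change from month 3 to month 6 is less exposed to early recovery, but within one arm it still has no comparator.

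The randomized control arm is there to remove this ambiguity, and the sentence does not use it. At stake is how durability is described, especially beyond 6 months: no between-arm analysis of CRQ or steps is named for the month 12 data.

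The control-arm clause raises a separate problem. If controls never receive home PR, there is no effect of it on them to assess. If they do receive it later, the plan has not said so, and the meaning of every between-arm comparison after that point changes.

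**Working it through.** **Step 1: the plan's own figure.** The challenged sentence gives no number. The nearest stated one is at least 80% power with 72 per arm for a CRQ difference of 0.5 (SD 1.0) or 1,000 steps (SD 2,000), in Statistical Analysis and Power. The standard error of a between-arm difference is 1.0 × √(2/72) = 0.167, so power at two-sided 5% is about Φ(0.5/0.167 − 1.96) = Φ(1.04) = 85%. Steps give the same result because 1,000/2,000 = 0.5. The stated figure is reproduced, and the same n and SDs are used below.

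**Step 2: what a within-arm change shows when the program does nothing.** Assumptions: 72 in the home arm; no program effect; mean recovery r, the same in both arms; SD of change equal to the plan's SD. The plan does not say its SD is an SD of change, and it gives no value for r, so a range is shown.

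Standard error of one arm's mean change = 1.0/√72 = 0.118.

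- P(mean change > 0) = Φ(r/0.118)
- P(mean change ≥ 0.5) = 1 − Φ((0.5 − r)/0.118)
- P(95% interval lies above 0) = Φ(r/0.118 − 1.96)

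| Recovery r (CRQ points) | Mean change > 0 | Mean change ≥ 0.5 (the plan's MCID) | 95% interval above 0 |
|---|---|---|---|
| 0 | 50% | about 0% | 2.5% |
| 0.25 | 98% | 1.7% | 56% |
| 0.5 | more than 99.9% | 50% | 99% |

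With an SD of change of 0.8 to 1.2, the last column runs from 76% to 42% at r = 0.25, and from about 100% to 94% at r = 0.5. For steps (SD 2,000), recovery of 250, 500 or 1,000 steps puts the interval above zero in 18%, 56% and 99%.

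**Step 3: the between-arm difference on the same data.** Its expectation is r − r = 0 for every r. Its 95% half-width before baseline adjustment is 1.96 × 0.167 = 0.33 CRQ points, against 1.96 × 0.118 = 0.23 within one arm. For steps the half-widths are 653 and 462. The interval is √2 times as wide, but it is centered on the program effect.

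**Step 4: which visits each analysis covers.**

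| Analysis of CRQ and steps | Month 3 | Month 6 | Month 9 | Month 12 |
|---|---|---|---|---|
| Scheduled assessment | yes | yes | no | yes (not under Aims 3b, 3c) |
| Between-arm analysis named | yes | yes (mixed model) | no | no |
| Descriptive change summary | yes | yes | named | not named |

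The descriptive sentence names a visit that is not scheduled and omits one that is.

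**Step 5: the two designs the text allows.** Under Phases 2 and 3 and the Conventional PR group section the trial is parallel, and the control-arm clause has no object. The Control/Wait label with its month 6 inventory, and the mention of treatment sequences, suggest that controls are coached between months 3 and 6. The clause would then have an object, but the control arm's change would be uncontrolled before-and-after data, and a home-minus-control difference at month 6 or later would compare two treated groups.

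**The case against.** The strongest reply has four parts.

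- **The summaries are untested.** They are declared descriptive and exploratory. This stands, and it limits the consequence. It does not turn a within-arm change into an estimate of an effect, and the plots by arm already supply the description. What the sentence adds is the causal reading.
- **Maintenance is already analyzed between arms.** This stands to 6 months. A reader might infer that every durability claim rests on within-arm change; the mixed model shows otherwise. The gap is this sentence's own interpretation and the month 12 data.
- **The text speaks of changes between visits, not only changes since baseline.** This also stands. The program runs 12 weeks, so a residual effect may well mean change after month 3, where early recovery matters less. The figures in Step 2 apply to change from baseline only. The lack of a comparator applies to both.
- **The control-arm clause makes sense under a wait-list.** It may. A reader might infer that the control arm's change can never bear on home PR; that holds only for the parallel design. The text supports neither reading consistently, and a fix that assumed one would settle the design without saying so.

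It is also fair to object that the interval-above-zero column describes a test the plan does not propose. It is shown only to indicate how convincing a null result could look.

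**Conclusion.** The point holds in a limited form. The plan reads a residual benefit, and an effect on controls, from summaries of change with no between-arm contrast. Where the change starts at the post-discharge baseline, it cannot distinguish program effect from recovery. With no program effect, recovery of 0.25 to 0.5 CRQ points would make the home arm's change positive in 98% or more of trials. It would reach the 0.5-point threshold in 1.7% to 50%. These figures rest on an assumed recovery common to both arms and on the plan's SD serving as an SD of change.

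A reader might go further and infer that the summary would show a lasting benefit in almost any post-hospital cohort. The documents do not support that. They neither state nor quantify recovery, and the plan itself assumes that 50% of controls are hospitalized or dead by 6 months, so steady improvement cannot be taken for granted.

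No primary or tested result depends on this sentence. It should still be corrected before analysis, because it invites a causal statement that the data it uses cannot support, and because it exposes an unresolved question about the design.

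**What to change.** 1. **Reconcile the design first.** State whether controls ever receive home PR and, if so, when. Bring the Phase 2, Phase 3, Conventional PR group, Questionnaires and Analyses text into agreement.
2. **Reconcile the visits.** Align month 9 with the visit schedule, and confirm that CRQ and ActiGraph are collected at month 12, given the shorter list under Aims 3b and 3c.
3. **If the design is parallel,** delete the control-arm clause. Estimate residual benefit as the home-minus-control difference in CRQ and steps, adjusted for baseline, at months 6 and 12 with 95% confidence intervals, and keep it exploratory.
4. **If controls cross over,** restrict the between-arm contrast to visits before crossover. If crossover follows month 3, the 6-month mixed model needs the same restriction, and the plan should say that residual benefit after that point has no randomized comparator.
5. **In either case,** present within-arm changes as trajectories and state that they are not interpreted as effects.

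The cost is SAP wording and one estimate per outcome per visit. No new data are needed on the month 3, 6 and 12 schedule. The downside is that the reported residual benefit may be smaller and its interval wider, by a factor of about √2 before baseline adjustment.
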